#### 2. STUDY OBJECTIVES AND ENDPOINTS

### 2.1 Study Objectives

## 2.1.1 Primary Objective

The primary objective is to compare the efficacy of C213 at doses of 1.9 mg and 3.8 mg (1.9 mg x 2 patches) to placebo in the acute treatment of cluster headache attacks.

## 2.1.2 Secondary Objectives

The secondary objective is to compare the safety of C213 at doses of 1.9 mg and 3.8 mg (1.9 mg x 2 patches) to placebo and to assess the dose-response relationship of C213 on

Protocol: CP-2019-001 Page 8 of 26

Final Version 1.0

efficacy and tolerability.

## 2.2 Study Endpoints

## 2.2.1 Efficacy Endpoints

The co-primary efficacy endpoints are:

• The proportion of subjects who achieve pain relief at 15 minutes and the proportion of subjects who achieve sustained pain relief from 15 minutes to 60 minutes. Headache pain is assessed using a 4-point scale (0 = none, 1 = mild, 2 = moderate, 3 = severe). Pain relief is defined by a decrease in pain from severe to mild or none without the use of acute rescue medication. Sustained pain relief requires a pain rating of mild or none at each timepoint from 15 minutes to 60 minutes without the use of acute rescue medication. The co-primary efficacy endpoints will compare the 1.9 mg and 3.8 mg treatment arms separately to placebo.

## Secondary efficacy endpoints:

- Proportion of subjects that achieve pain relief at 5, 10, 20 and 30 minutes post patch application
- Proportion of subjects that achieve sustained pain relief from 5 to 60 minutes and from 10 to 60 minutes post patch application
- Proportion of subjects that achieve pain freedom at 10 and at 15 minutes post patch application
- Proportion of subjects that achieve sustained pain freedom from 10 to 60 minutes and from 15 to 60 minutes post patch application
- Proportion of subjects using rescue therapy within 20 minutes post patch application
- Proportion of subjects able to perform their usual daily activities as assessed by the subject at 5, 10, 15, 20, 30 and 60 minutes post patch application

## 2.2.2 Safety Endpoints

Safety will be assessed by:

- Incidence of adverse events (AEs)
- Physical examination findings
- Vital signs including blood pressure
- Clinical laboratory determinations including coagulation studies
- Serum pregnancy and urine pregnancy for women of child-bearing potential
- 12-lead electrocardiogram (ECG) parameters

Protocol: CP-2019-001 Page 9 of 26 Final Version 1 0

- Assessment of concomitant medications
- Investigator visual skin assessments

## 3. OVERALL STUDY DESIGN AND PLAN

This is a phase 2/3, randomized, multicenter, double-blinded, placebo-controlled study that will investigate the efficacy and safety of C213 in the acute treatment of cluster headache attacks. Subjects who have consented and meet the entry criteria will be randomized to receive one of three blinded treatments. Approximately 120 subjects will be randomized. The study is to be conducted at approximately 13 investigational sites in the United States.

Qualified subjects will be randomized to the double-blind treatment period on Day 1 and will have up to 48 weeks to confirm and treat one cluster headache. Using an electronic diary (eDiary) to confirm the subject is experiencing a cluster headache, subjects will self-administer the patches and respond to questions in the eDiary until 1-hour post treatment.

The total duration of this study could be up to approximately 50 weeks over 3 visits, with up to 48 weeks of treatment duration and a variable length of screening (up to 10 days). This study will consist of a Screening visit (Visit 1, up to 1 week prior to randomization), Randomization visit (Visit 2, Day 1), up to a 48-week treatment period (Day 1 - Day 336), and End of Study/Early Discontinuation visit (Visit 3, 1-8 days post-treatment).

Screening activities may be completed over a period as short as one day or spread out over up to one week. At Visit 2, subjects will return to the site for additional baseline assessments and randomization (Day 1). If they meet all study randomization criteria, they will be randomly assigned in a 1:1:1 ratio to receive C213 1.9 mg administered as one active and one placebo patch, C213 3.8 mg administered as two active patches, or placebo administered as two placebo patches.

#### 3.1 Selection of Study Population

For a complete list of inclusion and exclusion criteria please refer to the initial protocol issued 27 June 2019, Amendment 1, dated 16 July 2019, Amendment 2, dated 01 October 2019 and Amendment 3, dated 15 April 2020.

## 3.2 Method of Treatment Assignment and Randomization

To be eligible for randomization and the double-blind period, subjects must meet all inclusion and no exclusion criteria. In addition, the following must be confirmed on the day of randomization:

1. Demonstrated ability to properly use the eDiary

Protocol: CP-2019-001 Page 10 of 26

Final Version 1.0

2. Willing to enter eDiary data to determine if he/she is experiencing a qualifying cluster headache attack and complete the eDiary questions after applying the patches

- 3. Demonstrated ability to apply the demonstration study drug patches
- 4. Confirmation of continuing good general health, or stable non-serious disease that in the opinion of the Investigator will not place the subject at risk

## 3.3 Treatment Blinding

This is a double-blind study. Unless otherwise specified, all study personnel are to remain blinded to study drug. Treatment assignments will not be revealed until all subjects have completed the study and the database has been finalized and closed.

If a medical emergency occurs and a decision regarding the subject's clinical treatment requires knowledge of the treatment assignment, the study blind may be broken for the specific subject. Unless the medical emergency is deemed to be life-threatening, the medical monitor must first be consulted before unblinding.

## 3.4 Minimization of Missing Data / Dropout rate

It is important to avoid missing data from clinical trials. The following strategies are designed to minimize drop-outs and missing data in this study:

- Minimizing the burden on subjects, with only three visits scheduled over the course of the trial (with reasonable visit window flexibility).
- Providing payment for subjects' time at clinic visits, as approved by the Institutional Review Board.
- Allowing rescue medication/therapy at or after 20 minutes post patch administration.
- Training of site personnel on emphasizing to subjects the importance of completing the eDiary assessments in order to minimize missing data.
- Employing an eDiary training module for subjects to complete prior to the distribution of the eDiary.
- Using alarms and reminder alerts for eDiary data entry.
- Instituting an eDiary reminder card for subject use that shows the timepoints when subjects need to enter data.
- Having a web portal available to site personnel where missing eDiary data can
  be easily identified so site personnel can be retrained on the importance of
  emphasizing to subjects the need to complete eDiary assessments, if
  necessary.

Due to the COVID-19 pandemic, the protocol was amended in April 2020 to allow for a visit 3 telemedicine visit. If any subjects cannot or elect not to be seen in clinic, the Visit

Protocol: CP-2019-001 Page 11 of 26

Final Version 1.0

3/End of Study Visit may take place via a virtual video (such as FaceTime, WhatsApp, Skype, Zoom). During this call, the Principal Investigator will assess for adverse events, skin reactions where C213 was applied, concomitant medication/rescue medication use, and drug accountability. For the subjects who are female of child-bearing potential, the sites will send a urine pregnancy test kit (monthly per protocol) and after dosing, verify that there is no pregnancy. In addition, the Sponsor, on a case by case basis, will consider allowing an 'out of window' Visit 3/End of Study Visit (in person). Any procedure such as vital signs, blood collection, and ECG which cannot be collected on site or remote will be indicated as 'not done' in both the source documents and eCRF, and if prompted, with a reason specified in the eCRF as due to the pandemic.

#### 4. ANALYSIS AND REPORTING

## 4.1 Interim Analysis

There is no interim analysis planned for this study.

#### 4.2 Final Analysis

All final, planned analyses will be performed after the last subject has completed all study assessments, all relevant study data have been processed and integrated into the analysis database, and the database has been locked.

Any post-hoc, exploratory analyses completed to support planned study analyses, which were not identified in this SAP, will be documented and reported in appendices to the CSR. Any results from these unplanned analyses (post-hoc) will also be clearly identified in the text of the CSR.

Protocol: CP-2019-001 Page 12 of 26

Final Version 1.0

## 5. SAMPLE SIZE DETERMINATION

The study is planned to enroll approximately 120 subjects total in a 1:1:1 randomization, that is, 40 subjects in each of the placebo, C213 1.9 mg, and C213 3.8 mg groups. It is anticipated that 20% of subjects receiving placebo and 55% of subjects receiving active treatment will achieve pain relief at 15 minutes and sustained pain relief from 15 minutes to 60 minutes post-dose. Based on a two-sided chi-square test with continuity correction and an alpha level of 0.05, 40 subjects per arm will provide approximately 80% power to detect this same difference between two treatment groups, assuming a 15% dropout rate.

Protocol: CP-2019-001 Page 13 of 26

Final Version 1.0

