### 12. CHANGES FROM PLANNED ANALYSIS

Due to insufficient enrollment numbers, the CMH test as described in the protocol for the primary and secondary analyses will not be performed. The protocol also describes a fixed sequential procedure to control for overall type 1 error. This will not be implemented since the actual number of randomized subjects is quite a bit less than planned and the pre-specified statistical analyses as described in the protocol cannot be performed.

Protocol: CP-2019-001 Page 25 of 26

Final Version 1.0

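### SAP Section 5 still gives 40 per arm and about 80% power as the only size and power statement, although Section 12 says enrolment fell well short of plan

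*SAP*

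**What the plan says.** SAP Section 5 plans for "approximately 120 subjects total in a 1:1:1 randomization", which makes 40 for every one of the three arms. It expects response in "20% of subjects receiving placebo and 55% of subjects receiving active treatment" on both co-primary endpoints. The calculation is "Based on a two-sided chi-square test with continuity correction and an alpha level of 0.05". After an allowance for 15% dropout, its conclusion is that "40 subjects per arm will provide approximately 80% power to detect this same difference between two treatment groups". This repeats Protocol Section 7.2. SAP Section 3 also still gives about 120 as the number to be randomised.

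SAP Section 12, in the same Version 1.0 dated 14 April 2021, reports that enrolment was insufficient and that "the actual number of randomized subjects is quite a bit less than planned". It gives this as the reason for not carrying out the Cochran-Mantel-Haenszel test or the fixed sequence.

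Section 9.1 replaces the planned test with Fisher's exact test of each dose against placebo, at the two-sided 0.05 level, on each co-primary endpoint. No section gives the number actually randomised, a revised power or an expected precision. Section 5 does not refer to Section 12.

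**The concern.** The SAP was finalised when the shortfall was already known and had already changed the primary test and the multiplicity plan. Its size and power section was left as it stood in the protocol. The only power figure in the document therefore belongs to a larger trial than the one to be analysed.

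This matters because Section 9.1 still runs significance tests at 0.05, and power governs how a non-significant result is read. A reader who takes the design from Section 5 could treat a null result as fair evidence against a 35-point difference. At a much smaller size it would be weak evidence. A statement of size and precision is also worth most before unblinding. The same statement made once results are known can look like an excuse for them.

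**Working it through.** **Inputs, all from SAP Section 5:** 40 randomised per arm; 15% dropout; response 20% on placebo and 55% on active, so d = 0.35; two-sided alpha 0.05; chi-square test with continuity correction. The test now planned is Fisher's exact test (SAP Section 9.1). The actual number randomised is not given; Section 12 describes it only in words.

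**Step 1: reproduce the stated power.**

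- Evaluable per arm: 40 × 0.85 = 34.
- Mean rate: (0.20 + 0.55)/2 = 0.375.
- SE under the null: √(2 × 0.375 × 0.625/34) = 0.1174.
- SE under the alternative: √((0.20 × 0.80 + 0.55 × 0.45)/34) = √(0.4075/34) = 0.1095.
- Power = Φ[(d − 1/n − 1.96 × SE₀)/SE₁] = Φ[(0.35 − 0.0294 − 0.2301)/0.1095] = Φ(0.826) = 79.6%.

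This agrees with the stated figure of about 80%. Run the other way, the continuity-corrected formula asks for 35 evaluable per arm, and 35/0.85 rounds up to 42 randomised, within 2 of the planned 40. The calculation is sound on its own inputs.

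**Step 2: does the change of test matter?** Exact enumeration of two binomials, counting outcomes that favour active with two-sided Fisher p ≤ 0.05, gives 81.5% at 34 per arm. The continuity-corrected chi-square, enumerated the same way, also gives 81.5%. The change to Fisher's test costs nothing at the planned size. Any loss of power comes from the smaller n.

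**Step 3: power and precision at smaller sizes.** The sizes below are assumed, for illustration. The total randomised that corresponds to each is 3 × n/0.85, using the SAP's own dropout rate. The half-width is 1.96 × √(0.4075/n).

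| Evaluable per arm (assumed) | Total randomised at 15% dropout | Fisher power, 20% vs 55% | 95% CI half-width (points) |
|---|---|---|---|
| 10 | about 35 | 19% | 40 |
| 15 | about 53 | 34% | 32 |
| 20 | about 71 | 53% | 28 |
| 25 | about 88 | 66% | 25 |
| 34 (as planned) | 120 | 81.5% | 21 |

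At 15 evaluable per arm the half-width (32 points) is close to the whole planned difference of 35 points. At 10 per arm (40 points) it exceeds it.

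**The case against.** The strongest defence is that Section 5 says nothing about the trial as enrolled. It is worded as a plan, the 80% is conditional on 40 per arm, and it restates the protocol's design basis correctly. Section 12 discloses the shortfall openly, and Section 8.1 will tabulate by arm the numbers randomised and in each analysis population. Someone who reads the whole SAP would not take 80% as the achieved power.

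Most of this stands. There is no calculation error and no concealment. What it does not answer is that the shortfall is disclosed only in words, and its effect on power and precision is not disclosed at all. The Section 8.1 table will appear with the results, not before them.

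A reader might go further in two ways that the documents do not support:

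- **That a non-significant result is now the more likely outcome even if the planned effect is real.** The number randomised is not given. Under the planning assumptions, Fisher power for one comparison is 48% at 18 evaluable per arm and 52% at 19, so this would hold only at about 18 or fewer. Nothing in either document puts the trial there.
- **That the 80% was overstated from the start because both co-primary endpoints must succeed.** Section 5 assumes the same 20% and 55% for both. Sustained relief from 15 to 60 minutes is nested within relief at 15 minutes, so equal rates mean the two endpoints coincide and joint power equals single-endpoint power. A lower joint figure needs a rate of relapse or rescue that the documents do not give. The requirement that both succeed for 3.8 mg also belongs to the protocol's fixed sequence, which SAP Section 12 drops.

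**Conclusion.** The point holds as one of stale reporting. The SAP's only size and power statement describes about 120 subjects, 40 per arm and about 80% power. The same version says that the trial did not reach that size.

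The extent of the loss cannot be fixed from the documents. On the SAP's own response rates, single-comparison power runs from about 19% at 10 evaluable per arm to 66% at 25, against 81.5% at the planned 34. These figures assume equal arms and that 20% versus 55% is true.

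There is an upper bound to note. If every randomised subject were evaluable, 3 × 34 = 102 randomised would still give about 80% power. That fits poorly with Section 12, where enrolment was judged too low for a test stratified by two headache subtypes, but the documents do not exclude it. No estimate or test changes as a result of this point. It affects how a null result can be interpreted.

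**What to change.** In SAP Section 5:

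1. Label 40 per arm and about 80% power as the original protocol design, and cross-refer to Section 12. Mark the figure of about 120 in Section 3 in the same way.
2. State the number actually randomised. While the study is blinded, the total is enough, or the expected number per arm under 1:1:1.
3. At that number, with an explicit allowance for subjects who will not enter the mITT population, give the Fisher's exact power for 20% versus 55% at two-sided 0.05 and the expected 95% confidence interval half-width for the difference.

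The cost is a few lines of text and one short calculation. It needs no new subjects or data, no change to any test, and no unblinding. The only price is that the stated power becomes less favourable if the evaluable number is below 34 per arm.

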## 6. ANALYSIS POPULATIONS

The following analysis populations are planned for this study:

• **Safety Population:** The safety population will include all subjects who received any amount of study drug. All safety analyses will be performed using this population, analyzed as treated.

• Modified Intention-To-Treat Population (mITT): All randomized subjects who have a qualifying headache and at least one post-application pain score recorded within the first 15 minutes post-application will be included in the mITT population. This is the primary population for efficacy analyses and subjects will be analyzed based on their randomized treatment.

Protocol: CP-2019-001 Page 14 of 26

Final Version 1.0

#### 7. GENERAL ISSUES FOR STATISTICAL ANALYSIS

## 7.1 General Statistical Methodology

Descriptive summaries will be provided where appropriate for each of the primary and secondary variables. In general, tables will summarize data by treatment group.

Baseline characteristic and safety tables will be completed for the Safety Population unless otherwise specified. Efficacy tables will be presented for the mITT Population.

Continuous, quantitative, variable summaries will include the number of subjects (N) with non-missing values, mean, standard deviation (SD), median, minimum, and maximum.

Categorical, qualitative, variable summaries will include the frequency and percentage of subjects who are in the particular category. In general, the denominator for the percentage calculation will be based upon the total number of subjects in the study population for the treatment group unless otherwise specified.

Baseline values are defined as the last non-missing measurement prior to patch administration. Change from baseline will be defined as the post-baseline visit value minus the baseline value.

Subjects are not supposed to change study sites; however, should this be necessary to allow a subject to continue in the study, subjects will be analyzed under the site where they were initially enrolled.

Study day after patch administration is defined as assessment date – patch administration date +1. Dates prior to patch administration are defined as assessment date – patch administration date.

All analyses will be performed using Statistical Analysis System (SAS®) Software version 9.3 or later.

## 7.1.1 Adjustments for Multiplicity and Other Alpha Control

There will be no adjustments made for multiplicity to control the overall type I error.

## 7.1.2 Data Handling for Subjects Who Withdraw from the Study

Subjects who withdraw/drop out from the study will have their early termination (ET) visit data collected within 1-8 days following the time of the subject's early termination. Safety data will be included in the Visit 3 end of study summaries as appropriate per the definition of the safety population. The subjects' efficacy data will be included in the efficacy analyses according to the definition of mITT.

## 7.1.3 Methods for Handling Missing Data

Missing pain and daily activities data for participants in the mITT population will be imputed via last observation carried forward (LOCF). Prior to imputing missing endpoint data for the endpoint sustained pain relief 15-60 minutes, pain relief will be assessed at each of the 15, 20, 30, and 60-minute timepoints that have data available. If any of these

Protocol: CP-2019-001 Page 15 of 26

Final Version 1.0

timepoints has a pain severity rating of moderate or severe, or if the subject has used a rescue medication/therapy, then the subject will be considered to have not achieved sustained pain relief and this endpoint will not be imputed. Otherwise, missing pain data will be imputed using LOCF. Missing data for all sustained pain relief and sustained pain freedom endpoints will be handled this way.

Missing safety data will not be imputed. Due to COVID-19, it is unavoidable that some subjects will be missing certain safety assessments, such as (but not limited to) Visit 3 clinical labs, vital signs, and ECG. This is because the Visit 3 occurred during the pandemic and telemedicine visit was necessary. Safety summaries will be generated using observed data, and missing safety assessments will be captured as protocol deviations.

Missing rescue medication data will be handled as described in section 7.2.4.4.

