#### 7.2.3 Sustained Pain Relief

The other co-primary efficacy endpoint is the proportion of subjects who achieve sustained pain relief from 15 minutes to 60 minutes post patch administration. Sustained pain relief requires a pain rating of mild or none at each timepoint from 15 minutes to 60 minutes without the use of acute rescue medication at any time during the 60 minutes post patch administration.

Protocol: CP-2019-001 Page 16 of 26

Final Version 1.0

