## 7.2.4.4 Rescue Medication/Therapy Use

A subject is considered to have taken a rescue medication by a given timepoint if the answer to the eDiary question, 'Did you take any medication, since your last diary entry, other than the patches you applied to treat your headache?' is answered Yes at that timepoint or any preceding timepoint. The specific medication/therapy is to be recorded as a concomitant medication in the CRF.

If rescue medication use data are missing for a given timepoint and there are no "Yes" responses at a previous timepoint, missing values will be imputed using the next available value (next observation carried backward). If rescue medication data are still missing after imputation, then it will be assumed a rescue medication was not taken. For the 60-minute timepoint, if rescue medication use data are missing at 60 minutes and there are no "Yes" responses at a previous timepoint, then the subject is considered not to have taken the rescue medication by the 60-minute timepoint.

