## 9.1.1 Sensitivity and Supporting Analyses

The primary analysis may be followed by a sensitivity analysis to investigate the impact of missing data on the treatment estimates.

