#### 9.1.1.1 C213 patients as failure and placebo as responder

If performed, this sensitivity analysis will be a repeat of the primary efficacy analysis where C213 patients with missing data will be imputed as non-responders/failures, and placebo patients with missing data as responders. Thus, for the co-primary outcome measure of pain relief at 15 minutes, C213 patients with a missing pain score at 15 minutes will be considered a treatment failure, and placebo patients with missing data at 15 minutes will be considered a responder. For the co-primary outcome measure of sustained pain relief, C213 patients with a missing pain score at any time from 15-60 minutes will be considered a treatment failure, and placebo patients with a missing pain score will be considered a responder only if all other pain scores within 15-60 minutes are not severe or are missing.

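### A diary that stops after one early mild or none score succeeds on both co-primaries, and the only missing-data check is optional and turns some observed placebo failures into sustained responses

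*SAP*

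**What the plan says.** - **Entry to analysis.** SAP 6 requires a qualifying headache and "at least one post-application pain score recorded within the first 15 minutes post-application". A score at 15 minutes itself is not needed.
- **Endpoint.** SAP 7.2.3: "Sustained pain relief requires a pain rating of mild or none at each timepoint from 15 minutes to 60 minutes", with no acute rescue during the 60 minutes.
- **Primary imputation.** SAP 7.1.3: "Missing pain and daily activities data for participants in the mITT population will be imputed via last observation carried forward (LOCF"). For sustained relief there is a safeguard: if any of the available 15, 20, 30 or 60-minute "timepoints has a pain severity rating of moderate or severe, or if the subject has used a rescue medication/therapy", the subject fails and nothing is imputed. Otherwise LOCF applies.
- **Rescue.** SAP 7.2.4.4 decides rescue use by the eDiary answer and fills gaps from the next available answer. Then: "If rescue medication data are still missing after imputation, then it will be assumed a rescue medication was not taken". It adds: "The specific medication/therapy is to be recorded as a concomitant medication in the CRF".
- **Sensitivity.** SAP 9.1.1: "The primary analysis may be followed by a sensitivity analysis". SAP 9.1.1.1 is also conditional on being performed. It fails C213 subjects with missing scores. For sustained relief, a placebo subject with a missing score is "considered a responder only if all other pain scores within 15-60 minutes are not severe or are missing". SAP 9.3 examines the change of time zero, not missing data.

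**The concern.** The second co-primary exists to show that relief lasts. For a subject who stops the diary early, it is decided by a score taken before the sustained window opens. Protocol Appendix 2 asks about pain and rescue in the same questionnaire, so a subject who stops loses both, and for a subject last seen at mild or none both defaults point to success.

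Protocol 7.4.1 leaves sensitivity analyses to the SAP, and the SAP supplies one that need not be run. If it is run, its placebo rule changes observed outcomes as well as missing ones, so it no longer tests the endpoint defined in 7.2.3. SAP 12 says that far fewer subjects were randomized than planned, so a few diaries could matter.

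**Working it through.** **1. The plan's own figure.** SAP 5 gives 20% vs 55%, two-sided 0.05, continuity-corrected chi-square, 40 per arm and 15% dropout. Evaluable per arm = 40 x 0.85 = 34. The pooled rate is 0.375.

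- SE0 = sqrt(2 x 0.375 x 0.625 / 34) = 0.1174
- SE1 = sqrt((0.20 x 0.80 + 0.55 x 0.45) / 34) = 0.1095
- z = (0.35 - 1/34 - 1.96 x 0.1174) / 0.1095 = 0.83, so power is 79.6%

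The stated 80% reproduces and is not in dispute.

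**2. The rules applied to example diaries.** Baseline is severe (Protocol 6.1.3.1) and no rescue is reported. Each cell gives 15-minute relief / sustained relief.

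| Diary | Primary (7.1.3, 7.2.4.4) | 9.1.1.1, placebo | 9.1.1.1, C213 |
|---|---|---|---|
| Mild at 5, then nothing | success / success | success / success | fail / fail |
| Severe at 5, mild at 10, then nothing | success / success | success / success | fail / fail |
| Severe at 5 and 10, then nothing | fail / fail | success / success | fail / fail |
| Mild at 15, 30 and 60; 20 missing | success / success | success / success | success / fail |
| Mild at 15, moderate at 20; 30 and 60 missing | success / fail | success / **success** | success / fail |
| Moderate at 15, 20 and 30; 60 missing | fail / fail | fail / **success** | fail / fail |

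Rows 1 and 2 are credited with no 15-60 minute observation, because the 7.1.3 safeguard has nothing to act on. Row 3 shows LOCF working the other way. The bold cells are observed failures turned into responses; in the last row the subject fails relief at 15 minutes yet has relief sustained from 15 minutes.

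**3. Size of the placebo-rule conflict.** One subject is 1/34 = 2.9 points, 1/20 = 5.0 or 1/15 = 6.7. The sizes 20 and 15 are assumed, because SAP 12 gives no number. As an illustration, take 19/34 C213 vs 7/34 placebo (Fisher p = 0.0055). Moving 1, 2, 3 or 4 placebo failures to responder gives p = 0.0125, 0.0258, 0.0490 or 0.0866.

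**4. False successes under LOCF, sustained relief only.** Let m be the share of responders who stop the diary and f the share of those who relapse or take rescue. With both equal across arms, the gain in the difference is 0.55mf - 0.20mf = 0.35mf.

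| m | f = 25% | f = 50% | f = 100% |
|---|---|---|---|
| 5% | 0.4 | 0.9 | 1.75 |
| 10% | 0.9 | 1.75 | 3.5 |
| 15% | 1.3 | 2.6 | 5.25 |

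These are percentage points against a planned 35. The gain is zero if no stopper relapses, and it reverses if mf on placebo exceeds 0.55/0.20 = 2.75 times that on C213. False failures (row 3) are not in this formula, so it is not the net LOCF effect. In the same 19/34 vs 7/34 illustration, recoding 1, 2, 3 or 4 C213 early-stop successes as failures gives p = 0.0112, 0.0214, 0.0392 or 0.0684.

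**5. How extreme 9.1.1.1 is.** Suppose 15% of each arm has a gap unrelated to outcome.

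- Gaps as non-response in every arm: 0.55 x 0.85 = 46.75% vs 0.20 x 0.85 = 17%, a difference of 29.75 points.
- Every placebo gap credited (an upper bound for sustained relief): 46.75% vs 17% + 15% = 32%, a difference of 14.75 points.

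The exact chance of Fisher p <= 0.05 is 68.6% vs 17.8% at 34 per arm, and 42.3% vs 9.5% at 20. This describes the severity of the bound, not the effect of the conflict in step 3.

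**The case against.** **LOCF is not one-sided.** It carries early moderate and severe scores forward as failures. Median Tmax is 20 minutes for 1.9 mg and 17.5 for 1.9 mg x 2 (Protocol Table 1), so some early stoppers scored as failures may have had relief soon after. This stands. A reader might infer that the primary analysis is biased toward C213; the documents do not support that.

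**A worst-case analysis is meant to be harsh, and this one works against C213.** That also stands. A reader might infer that the check hides a LOCF gain, or that step 5 measures the defect. Neither follows. Filling missing values pessimistically is legitimate, but overriding an observed moderate score is a different matter, and the objection does not answer it.

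**Optional wording is harmless if nothing is missing.** With no gaps, the check reproduces the primary result. That is equally a reason to commit to it.

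**Rescue.** A reader might infer that 9.1.1.1 ignores rescue use, or that rescue recorded in the CRF must override the diary. The first is weak, because 9.1.1.1 is a repeat of the primary analysis and the rescue rule reasonably carries over. On the second, 7.2.4.4 decides by the eDiary, the SAP's medication conventions (7.3.1, 11.1) use dates and not clock times, and 7.2.4.4 also governs several secondary endpoints.

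**Gaps may be few.** The alarms, training, reminder card and portal in SAP 3.4 should help, and the by-subject rescue listing in 9.2 gives some visibility. Neither counts imputed outcomes nor tests their effect.

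**Conclusion.** Three things hold on the text alone: early-stop diaries with a mild or none score succeed on both co-primaries; the one missing-data check is optional; and its placebo rule counts observed moderate pain as sustained relief, contrary to 7.1.3 and 7.2.3. The last is an error as written, worth 2.9 points per affected placebo subject at 34 per arm and more in a smaller trial. It affects only the sensitivity analysis and can only disadvantage C213.

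The net LOCF effect on the treatment difference is undetermined in size and direction. The 0.4 to 5.25 point range covers false successes on sustained relief only, under assumed stopping and relapse rates and the planned 55% and 20%. The p-values rest on assumed counts. The point should be fixed, but it does not show that the primary result is wrong.

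**What to change.** Keep LOCF as the primary rule.

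1. **SAP 9.1.1.1:** require the placebo subject's other observed 15-60 minute scores to be mild or none, instead of merely not severe. State that any observed moderate or severe score, or reported rescue use, is failure for sustained relief in both arms, as in 7.1.3.
2. **SAP 9.1.1 and 9.1.1.1:** replace the permissive wording with a commitment that the analysis will be done.
3. **SAP 9.1.1:** add a sensitivity analysis of both co-primaries in which trailing missing diary data (no later entry) are non-response in every arm, with other gaps handled as in 7.1.3. Label it a conservative bound: it equals the f = 100% case in step 4, so losing significance under it would not prove that LOCF credits were false. Report imputed successes and imputed failures by arm and endpoint; those counts show how much the result depends on imputation.

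Rescue recorded in the CRF should not become an endpoint rule. At most, list subjects whose CRF rescue record disagrees with the eDiary.

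The cost is SAP wording, one further analysis and one count table. The primary rule and test are unchanged. The downside is that the added results may look less favourable than LOCF.
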